Appendix 2. Cockcroft-Gault Calculation

Creatinine Clearance (estimated) / Conventional mL/min =

$$((140 - \text{Age (years)}) \times \text{Weight (kg)} \times \text{Factor}^a) / (72 \times \text{Serum Creatinine (mg/dL)})$$

^a Factor is equal to 0.85 in females and 1.00 in males.

Appendix 3. Prohibited Concomitant Medications

Subjects taking certain medications for PsA, and deriving inadequate benefit from them, may enter the study after a sufficient washout period for that medication. Subjects receiving certain medications for psoriasis may enter the study after a sufficient washout period for that medication ([Section 4.1.2](#), criterion #3).

All **biologic DMARDs** are prohibited and require a specific washout period (as listed in the protocol or based upon Sponsor review) prior to first dose of study treatment. Subjects on TNF inhibitors must discontinue according to the following criteria:

- Etanercept (Enbrel[®]): Discontinued at least 4 weeks prior to the first dose of study drug;
- Adalimumab (Humira[®]): Discontinued at least 10 weeks prior to first dose of study drug;
- Infliximab (Remicade[®]): Discontinued at least 8 weeks prior to the first dose of study drug;
- Golimumab (Simponi[®]): Discontinued at least 10 weeks prior to the first dose of study drug;
- Certoluzimab (Cimzia[®]): Discontinued at least 10 weeks prior to the first dose of study drug.

Patients entering from studies in which adalimumab (Humira[®]) was administered in a double-blind manner must have a minimum of 1 week washout after their last injection (placebo or adalimumab) and prior to their first dose of tofacitinib in this study.

Subjects receiving biologic agents for the treatment of psoriasis must discontinue according to the following criteria:

- Ustekinumab (Stelara[®]) must be discontinued for at least 12 weeks prior to first dose of study drug;
- Alefacept (Amevive[®]) must be discontinued for at least 8 weeks prior to first dose of study drug;
- Efalizumab (Raptiva[®]) is prohibited per exclusion criterion #12.

Other biologic agents used as DMARDs or used for the treatment of psoriasis are prohibited and require a 6 month washout period unless otherwise specified above.

The following traditional non-biologic DMARDs are prohibited: azathioprine, cyclosporine, mizoribin, tacrolimus and tetracycline (used as a DMARD). In the sub-study, sulfasalazine and leflunomide are considered prohibited medications.

All of these prohibited non-biologic DMARDs require a 4 week washout period prior to first dose of study drug.

Injectable (intravenous, intramuscular) corticosteroids are prohibited during the study ([Section 4.1.1](#)); intra-articular injections of corticosteroids are only permitted as rescue medication ([Appendix 6](#)).

Medications used to treat psoriasis are prohibited ([Section 4.1.2](#)). This also includes topical treatments that could affect psoriasis, eg, corticosteroids, tars, keratolytics, anthralin, vitamin D analogs, and retinoids and must be discontinued at least 2 weeks prior to first dose of study drug. Also prohibited is ultraviolet B (UVB) (narrowband or broadband) phototherapy that must be discontinued at least 2 weeks prior to first dose of study drug. Psoralens + ultraviolet A (UVA) phototherapy (PUVA) must be discontinued at least 4 weeks prior to first dose of study drug.

- Exceptions- the following topical treatments are allowed: non-medicated emollients for use over the whole body; topical steroids including hydrocortisone and hydrocortisone acetate $\leq 1\%$ for the palms, soles, face and intertriginous areas only; tar and salicylic acid preparations for the scalp only and shampoos free of corticosteroid for the scalp only.

All non-biologic Investigational Drugs or marketed treatments for PsA or psoriasis not otherwise specified are prohibited (unless otherwise approved by the Sponsor) and require a 4 week (≥ 5 half-lives) washout period prior to first dose of study treatment ([Section 4.1.2](#)).

All other prohibited drugs (see below) require at least a 7 day or 5 half-life (whichever is longer) washout period prior to the first dose of study treatment. In the table version below, those drugs requiring washout longer than 7 days are in bold and italicized. Note: efavirenz, nevirapine, barbiturates, carbamezipine, Phenobarbital, St. John's Wort, rifabutin and rifapentene should be discontinued at least 30 days prior to first dose of study drug based on half life of these drugs, and that amiodarone should be discontinued at least 290 days prior to the first dose of study drug based on a half-life of 58 days. **For a medical condition (other than PsA) where it is important for the subject's safety to continue a prohibited drug, and where there is no study-permitted alternative, the subject must not participate in this study. Note that the list of prohibited medications includes, for example, anti-seizure and antiviral drugs for chronic use.**

- Topical (including skin or mucous membranes) application of antibacterial (eg, clarithromycin, erythromycin and norfloxacin) and antifungal (fluconazole, ketoconazole, clotrimazole and itraconazole) medications is permitted.
- Potent inhibitors and inducers of CYP3A (shown below) are not permitted in the study except in emergency situations requiring no more than one day of administration or as approved by the Pfizer Study Clinician.

Potent CYP3A Inhibitors	Potent CYP3A Inducers
HIV antivirals: -indinavir (Crixivan) -nelfinavir (Viracept) -ritonavir (Kaletra, Norvir)	efavirenz (Sustiva)
clarithromycin (Biaxin, Prevpac)	nevirapine (Viramune)
itraconazole (Sporanox)	barbiturates
ketoconazole (Nizoral)	carbamazepine (Carbatrol, Tegretol)
nefazodone (Serzone)	modafinil (Provigil)
	phenobarbital
	phenytoin (Dilantin, Phenytek)
	rifabutin (Mycobutin)
	rifampin (Rifadin, Rifamate, Rifater)
	rifapentine (Priftin)

- Subjects may be initiated on moderate inhibitors (except amiodarone) and inducers (shown below), as required, if the total duration of treatment lasts less than or equal to 7 days.
- Consumption of juice from grapefruit, pomelos and Seville oranges is permitted up to 8 oz or 236 mL (total) in a day. It is recommended to separate their coadministration with study medication by at least ± 1 hour.

Moderate CYP3A Inhibitors	Moderate CYP3A Inducers
HIV antivirals: - atazanavir (Reyataz) - delavirdine (Rescriptor) - saquinavir (Fortovase)	St. John's wort
amiodarone (Cordarone, Pacerone)	
cimetidine (Tagamet)	
clotrimazole	
diethyl-dithiocarbamate	
diltiazem (Cardizem, Tiazac)	
erythromycin	
fluconazole (Diflucan)	
fluvoxamine (Luvox)	
grapefruit or grapefruit-related citrus fruits, juices (eg, Seville oranges, pomelos)	
mibefradil	
mifepristone (Mifeprex, RU486)	
norfloxacin (Shibroxin, Noroxin)	
verapamil (Calan SR, Covera HS, Isoptin SR, Tarka, Verelan)	
voriconazole	

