1.2.5. Clinical Pharmacokinetics

The pharmacokinetic (PK) profile of tofacitinib is characterized by rapid absorption, rapid elimination (terminal half-life of ~3 hours) and dose proportional PK. Co-administration with a high fat meal increased the tofacitinib AUC by 14% and decreased C_{max} by 26%; no dosage adjustments or meal restrictions during chronic dosing are warranted. The clearance mechanisms for tofacitinib in humans appear to be both non-renal and renal excretion of the parent drug, the former accounting for approximately 2/3 of the total clearance. The

metabolism of tofacitinib appears to be primarily mediated by CYP3A4 with minor contribution from CYP2C19 as suggested by data from poor metabolizers of CYP2C19. The PK of tofacitinib is similar between Caucasians and Japanese healthy volunteers.

In vitro studies have shown that tofacitinib does not significantly inhibit the major drug metabolizing CYPs, indicating a low potential for tofacitinib to increase the exposure of other drugs. This was demonstrated in a clinical study where tofacitinib did not have an effect on the pharmacokinetics of an oral dose of midazolam (a highly sensitive CYP3A substrate) in healthy volunteers. On the other hand, inhibitors and inducers of CYP3A4/5 are likely to alter the disposition of tofacitinib. Co-administration of tofacitinib with fluconazole, a moderately potent inhibitor of CYP3A4 and a potent inhibitor of CYP2C19, resulted in 79% and 27% increases in the AUC and C_{max} of tofacitinib, respectively. Co-administration of tofacitinib with methotrexate had no effect on the PK of tofacitinib and resulted in an approximate 10% decrease in the AUC of methotrexate. The extent of decrease in methotrexate exposure does not warrant modifications to the individualized dosing of methotrexate. Co-administration of tofacitinib with cyclosporine and oral tacrolimus, moderate and weak CYP3A4 inhibitors, respectively, resulted in increases of 73% and 21% in AUC_{inf} of tofacitinib. In both cases, tofacitinib C_{max} was decreased slightly; ratio 91%, for tacrolimus and 83%, for cyclosporine.

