Consistent with the ~30% contribution of renal clearance to the total clearance of tofacitinib, mean exposure in end stage renal disease (ESRD) subjects (on a non-dialysis day) was approximately 40% higher compared with historical healthy subject data. In contrast, in a separate study, mean exposure was approximately 125% higher in subjects with severe renal impairment compared with healthy subjects. Mild and moderate renally impaired subjects had 37% and 43% higher exposure, respectively, compared with healthy subjects.

Based on these data, subjects with estimated creatinine clearance <40 mL/min will be excluded from this study as will concomitant use of moderate to potent inhibitors of CYP3A4/5.

Further clinical pharmacology background information on tofacitinib can be found in the current version of the tofacitinib Investigator's Brochure.

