1.2.7. Dose Selection Rationale

Doses of tofacitinib (5 mg BID and 10 mg BID) that were previously demonstrated to be efficacious in the RA and psoriasis Phase 2 development programs are currently being, or have been, studied in their respective Phase 3 programs. These tofacitinib doses of 5 mg BID and 10 mg BID will also be evaluated in this long-term extension study in PsA subjects.

Tofacitinib doses of 5 and 10 mg BID were selected for the Phase 3 programs for each of these indications based on modeling of extensive Phase 2 dose-response data. The Phase 2 programs include 5 studies in RA patients (A3921019, A3921025, A3921035, A3921039 and A3921040) and 1 study in psoriatic patients (A3921047). The dose selection for RA was based primarily on study A3921025, which evaluated 5 doses (1, 3, 5, 10 and 15 mg BID tofacitinib and placebo for up to 24 weeks). The dose selection for psoriasis was based primarily on study A3921047 in which 3 doses of tofacitinib were studied (2, 5 and 15 mg BID) for up to 12 weeks.

For each program, a review of several efficacy and safety outcomes was performed to identify key drivers for dose selection. The selection of doses for RA was based on longitudinal dose-response modeling of the ACR20, ACR50 and ACR70 responses for efficacy and changes in hemoglobin (and associated anemia incidence) for safety. Similarly, the selection of doses for psoriasis was based on modeling of PASI75 and PGA endpoints for efficacy and changes in hemoglobin for safety. Dose selection was principally based on the probability of achieving a clinically meaningful target effect (PTE), where the target effect was defined in terms of a placebo-adjusted difference at a specific time point that is considered to be clinically meaningful. Doses that were considered for Phase 3 were those that achieved a PTE of approximately 50% or higher on each endpoint. The relationships between tofacitinib dose and PTE are displayed in [Figure 2](#) and [Figure 3](#) for RA and psoriasis, respectively. As shown in the figures, the 5 and 10 mg BID doses met the criteria (PTE of approximately 50% or higher on nearly all endpoints) for progression into Phase 3 for both indications.

Figure 2. Probability of Achieving Target Effect for Efficacy (ACR20, ACR50 and ACR70) and Safety (Incidence of Anemia) Endpoints Based on Modeling of Study A3921025 Data in RA Patients

[figure not shown]
[figure not shown]

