3. STUDY DESIGN

This is a Phase 3, long-term, open-label extension study designed to evaluate the safety, tolerability and efficacy of tofacitinib in subjects with active PsA who have previously participated in randomized PsA clinical studies with tofacitinib. For subjects who complete participation in such a randomized clinical study with tofacitinib, the final visit of the qualifying study can be combined with the screening and baseline visit for this study. Additional assessments and inclusion/exclusion criteria are required for subjects who enroll >14 days after completing treatment in their qualifying study. In this case, a separate screening visit to determine subject eligibility is required followed by a baseline visit.

All eligible subjects from qualifying studies A3921091 and A3921125 will receive open-label tofacitinib 5 mg BID upon entry into A3921092. Subjects from A3921091 will receive first dose of study medication ≥ 1 week after last injection of study medication in that qualifying study. Tofacitinib dose may be increased to 10 mg BID at study visits if, based upon investigator's discretion, subjects receiving tofacitinib 5 mg BID would benefit from a higher dose and are not experiencing any tofacitinib-related adverse events, including abnormalities in laboratory parameters that are judged to be related to tofacitinib. Tofacitinib dose may be decreased (ie, 10 mg BID to 5 mg BID) for safety reasons at any time during the study. Treatment duration for subjects participating in the LTE study is approximately 3 years (36 standardized 4-week months). Subjects participating in the sub-study may have up to an additional 1 year (12 standardized 4-week months) of treatment for a maximum potential total of approximately 4 years (48 standardized 4-week months).

At various time points in this trial, safety measurements, including physical examination, clinical laboratory tests, adverse event monitoring, electrocardiograms (ECGs) and vital signs will be performed. All subjects will be monitored for clinical evidence of response of PsA to treatment. Health Outcome Measures (ie, Patient Reported Outcomes assessment questionnaires for pain, quality of life, physical function, fatigue, work limitations, health care resource utilization and health status) will also be performed at various time points in this trial. In addition, subjects will be monitored for serious infections, lymphadenopathy and lymphoproliferative disorder (LPD).

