5. STUDY TREATMENTS

For the purposes of this study, and per International Conference on Harmonisation (ICH) guidelines, investigational product is defined as a pharmaceutical form of an active ingredient or placebo being tested or used as a reference/comparator in a clinical trial, including a product with a marketing authorization when used or assembled (formulated or packaged) in a way different from the approved form, or when used for an unapproved indication, or when used to gain further information about an approved use (ICH E6 1.33).

Study drug will be dispensed to subjects to self-administer after appropriate training and specific written instructions are provided. Tofacitinib will be taken orally 5 mg BID (approximately every 12 hours). The investigator has the option to increase the dose to 10 mg BID in those subjects who are receiving 5 mg BID and, in the investigator's opinion, has PsA symptoms that are not adequately controlled. Changes in the dose are only permitted at scheduled study visits, unless a reduction to 5 mg BID is required due to safety abnormalities as outlined in [Appendix 4](#). Study treatment will continue in the LTE portion of the study until the subject discontinues from the study or has received approximately 3 years (36 standardized 4-week months) of treatment.

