5.3. Drug Supplies

Each tofacitinib bottle will be labeled as appropriate for this open-label study. Study medication will be taken according to the instructions provided to the subject. The specific subject instructions will also direct the subject to bring the study medication bottle(s) to the clinic on study visit days. Any permitted dose adjustments that may occur between scheduled study visits (ie, dose reduction for safety reasons) must be clearly documented on the subject's chart and verified for start date and dose when the subject returns for their next scheduled visit.

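### Appendix 3 allows up to 7 days of systemic fluconazole on tofacitinib 10 mg BID with no required dose reduction, although Section 1.2.5 reports a 79% rise in mean AUC and says such inhibitors are excluded

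*Protocol*

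**What the plan says.** Protocol Appendix 3 grades CYP3A inhibitors by potency. Potent ones are barred except for a one-day emergency or with the study clinician's approval. For moderate ones it says: "Subjects may be initiated on moderate inhibitors (except amiodarone) and inducers (shown below), as required, if the total duration of treatment lasts" 7 days or less. Fluconazole is on the moderate list. Topical antifungals are permitted separately, so the 7-day rule concerns systemic use. No tofacitinib dose is named and no reduction is required.

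Section 1.2.5 describes tofacitinib PK as dose proportional. It reports that fluconazole "resulted in 79% and 27% increases in the AUC" and Cmax respectively. The same section bars subjects with creatinine clearance below 40 mL/min, "as will concomitant use of moderate to potent inhibitors of CYP3A4/5", and does not mention the Appendix 3 allowance.

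On dose changes, Section 3 says: "Tofacitinib dose may be decreased (ie, 10 mg BID to 5 mg BID) for safety reasons at any time during the study". Section 5.8 also allows reduction for any safety-related issue. Section 5 is narrower: "Changes in the dose are only permitted at scheduled study visits, unless a reduction to 5 mg BID is required due to safety abnormalities" of the kind set out in Appendix 4. Appendix 4.2 lists adverse events and confirmed laboratory abnormalities, and drug interactions are not among them. Section 5.3 treats such reductions as possible between visits: "Any permitted dose adjustments that may occur between scheduled study visits (ie, dose reduction for safety reasons) must be clearly documented". Increases to 10 mg BID are limited to scheduled visits (Section 5.8, Appendix 4.2).

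For infections, Section 8.6.2 lets tofacitinib be held during antimicrobial treatment but does not require it. If a subject on 10 mg BID is held, Appendix 4.2 restarts at 5 mg BID. Serious infections and significant opportunistic infections lead to withdrawal (Section 7.6.9.2, Appendix 4.3).

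**The concern.** The introduction and the operative medication rule disagree on whether a moderate inhibitor may be used at all. Appendix 3 governs what sites do, and it permits fluconazole at either tofacitinib dose. On the protocol's own PK figure, a subject on 10 mg BID would have a mean AUC above that of the highest dose in the studies on which dose selection mainly rested. Fluconazole is an antifungal, so the rise would usually come while an infection is being treated, and infection is a listed risk of tofacitinib.

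The existing safeguards leave one case open: a subject on 10 mg BID with a non-serious infection whose investigator neither holds nor reduces the drug. An investigator who wants to reduce as a precaution finds Sections 3 and 5.8 permissive. Section 5, read with Appendix 4.2, leaves it unclear whether a preventive change between visits is allowed. At stake is the safety of that individual subject.

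**Working it through.** The documents give no dose-equivalent figure to reproduce, so the check converts the reported ratios.

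**Inputs**
- AUC ratio 1.79 and Cmax ratio 1.27 with fluconazole; dose-proportional PK (Section 1.2.5).
- Maximum main-study dose 10 mg BID (Appendix 4.2); sub-study dose fixed at 5 mg BID (Appendix 10).
- Top dose 15 mg BID in both main dose-selection studies (Section 1.2.7). This includes the RA study, "which evaluated 5 doses (1, 3, 5, 10 and 15 mg BID tofacitinib and placebo for up to 24 weeks".
- Renal impairment: "Mild and moderate renally impaired subjects had 37% and 43% higher exposure, respectively, compared with healthy subjects" (Section 1.2.5).
- Treatment of 36 months of 28 days, 36 × 28 = 1008 days; most visits are three such months apart, 3 × 28 = 84 days.

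**Exposure on 10 mg BID.** Equivalent dose = dose × ratio.
- AUC: 10 × 1.79 = 17.9 mg BID; 17.9/15 = 1.19.
- Cmax: 10 × 1.27 = 12.7 mg, below 15 mg.
- Moderate renal impairment without fluconazole: 10 × 1.43 = 14.3 mg BID; 17.9/14.3 = 1.25.
- Duration: 7/1008 = 0.7% of treatment days for one course.

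**Dependence on the ratio.** Section 1.2.5 gives neither the fluconazole dose and duration nor the tofacitinib dose behind the 79%. AUC passes the 15 mg BID level only if the ratio exceeds 15/10 = 1.5. From no interaction to the reported figure, the equivalent dose runs from 10 to 17.9 mg BID, and a rise of less than 50% would leave it below 15.

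**Exposure on 5 mg BID.** 5 × 1.79 = 8.95 mg BID, and 8.95/10 = 89.5% of the usual 10 mg BID AUC. It would pass the 10 mg BID level only at a ratio above 10/5 = 2.

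**Trade-off of a reduction**, in units of one day's usual 10 mg BID AUC, assuming that inhibition ends with the course:
- Excess from a 7-day course left unreduced: 7 × 0.79 = 5.5.
- Shortfall during a reduced course: 7 × (1 − 0.895) = 0.7.
- Shortfall if return waits a full visit interval: (84 − 7) × 0.5 = 38.5 more.

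Most of the cost of reducing therefore comes from a late return.

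**The case against.** The strongest reply is that this is a deliberate, bounded choice. The sponsor reports the interaction itself, grades inhibitors by potency, caps moderate ones at 7 days and singles out amiodarone. Investigators may already hold or reduce, subjects must report medication changes (Section 4.4), and the more dangerous infections end treatment. All of that stands, and it confines the gap to non-serious infections where neither step was taken.

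The benchmark is also open to challenge, and rightly. A reader might infer that 17.9 mg BID breaches a limit or exceeds every dose studied. The documents support neither. The 10 mg BID maximum caps dose and not exposure, and nothing makes 15 mg BID a ceiling. Section 1.2.7 names four other RA Phase 2 studies without giving their doses. The RA study ran 15 mg BID for up to 24 weeks, and moderate renal impairment already implies about 14.3 mg BID-equivalent for as long as treatment lasts.

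A reader might also infer actual harm, or distorted safety rates or sub-study results. No section shows harm from a course this short. The SAP summarises the main study as one flexibly dosed group, and the sub-study is fixed at 5 mg BID.

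What the reply does not remove is the disagreement between Section 1.2.5 and Appendix 3, or the doubt that Section 5 casts on a preventive reduction.

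**Conclusion.** The point holds as a minor, optional safety improvement for main-study subjects on 10 mg BID. Appendix 3 permits systemic fluconazole for up to 7 days without a required reduction, while Section 1.2.5 reports a 79% AUC rise and says such inhibitors are excluded.

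The size is a mean AUC like that of about 17.9 mg BID, 1.19 times the 15 mg BID level, for about 0.7% of treatment days per course. This rests on dose-proportional PK and on the reported mean ratio applying to the course actually given. The number of subjects on 10 mg BID is not stated, so the frequency cannot be judged. The case for acting is that a step down keeps about 90% of the usual AUC during the course and fits the temporary reductions that Appendix 4.2 already allows.

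**What to change.** - **Reduction.** Add to Appendix 3, and to the list in Appendix 4.2 of adjustments allowed at any time, that a main-study subject on 10 mg BID who starts systemic fluconazole takes 5 mg BID for the course. Cross-reference this in Sections 5 and 5.8 as a permitted change between visits.
- **Return.** Allow 10 mg BID again only after fluconazole has stopped and the infection has resolved, with no tofacitinib-related adverse event or laboratory abnormality. This would be at the next scheduled visit, or earlier at an unplanned visit with Sponsor agreement. Do not borrow the Appendix 3 washout periods, which govern the time before first study dose.
- **If tofacitinib is held** for the infection, the existing restart at 5 mg BID applies.
- **Clerical.** In Section 1.2.5, qualify the exclusion with *except as permitted in Appendix 3*.

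For the other listed moderate inhibitors the documents give no figure, so leave reduction to the investigator.

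**Cost.** The subject was raised to 10 mg BID for inadequate control and spends a short time at 5 mg BID after the course, or up to about 84 days in all if return waits for the next scheduled visit. The unplanned-visit route limits this. The 10 mg dose is two tablets, so no new supply is needed. Compliance should be counted against the documented reduced dose. An 84-day supply is 84 × 4 = 336 tablets and each reduced day uses two fewer, so an unadjusted count falls below 80% after 0.2 × 336/2 = 33.6 days. The text change needs ethics approval (Section 12.1) and can wait for the next amendment.
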